3.2.5 UNSCHEDULED VISITS

If a subject returns for an unscheduled visit (i.e., adverse event, adverse event follow up), the subject will undergo the assessments and procedures listed in the schedule of events table in section 1.3.

3.3 EXPLORATORY ANALYSIS

In addition to the daily pain assessment and rescue medication intake obtained through the EMA at the end of the day, subjects' pain/pressure will be assessed on a scale of 1 to 10 at one other random time throughout the day. This will allow for collection of data from subjects in real time in their natural environments.[14, 15]

3.4 JUSTIFICATION FOR DOSE

The recommended dosing per the approved drug package insert provided by the manufacturer is 70mg or 140mg once monthly. Improved efficacy with similar adverse effect profile has been demonstrated for the 140 mg dose versus the 70 mg dose based on the STRIVE trial.[9]

3.5 END OF STUDY DEFINITION

The study will end when the last subject completes the last study visit on Day 180.

4 STUDY POPULATION

4.1 INCLUSION CRITERIA

1. Adults 18 years of age or older presenting to Duke Head & Neck Surgery and Communications Sciences clinic for evaluation of rhinosinusitis and/or facial pain or pressure.
2. Symptoms are present at least 10 days a month for the last 3 months as reported by subject.
3. Symptoms must include midfacial pain or uncomfortable pressure (may be unilateral or bilateral), which is defined as pain in the regions overlying the maxillary, ethmoid, frontal sinuses either together or individually.
4. Nasal endoscopy in the last three months shows no signs of inflammation (i.e. thick drainage, polyps, watery edema in the middle meatus or spheno-ethmoid recess (mild edema permitted).
5. Sinus CT scan or MRI within 12 months of enrollment during a symptomatic period shows no more than scattered minimal mucosal edema or mucous retention cyst with patent infundibula bilaterally. For subjects with a CT scan more than 12 months old or just an MRI, a CT will be repeated for study purposes. For patients with CT scans less than 12 months old, a CT will be repeated for study purposes if the subject has changes in symptoms suggestive of sinusitis.
6. Ability to read/write English.
7. Has a smart phone and access to the internet.

4.2 EXCLUSION CRITERIA

1. Hypersensitivity to erenumab or to any of the drug components (acetate, polysorbate, and sucrose).
2. Previous exposure to erenumab or any other -CGRP inhibitor in the six months prior to enrollment.
3. Allergy to latex.
4. Inability to differentiate facial pain from other headaches.
5. Non-English speaking or unable to provide written informed consent.
6. On a preventative migraine medication (see below) during the 30 day lead-in period:
 - Category 1: Divalproex sodium, sodium valproate
 - Category 2: Topiramate
 - Category 3: Beta blockers (for example: atenolol, bisoprolol, metoprolol, nadolol, ebivolol, pindolol, propranolol, timolol)

- Category 4: Tricyclic antidepressants (for example: amitriptyline, nortriptyline, protriptyline)
- Category 5: Serotonin-norepinephrine reuptake inhibitors (for example: venlafaxine, desvenlafaxine, duloxetine, milnacipran)
- Category 6: Flunarizine, verapamil
- Category 7: Lisinopril, candesartan

7. Received botulinum toxin (Botox) to the head and neck for migraines in the last four months.
8. More than one major open surgery of the nose or sinuses for sinonasal cancer.
9. History of uncontrolled or unstable blood pressure.
10. History of liver failure.
11. History of metastatic malignancy in the last five years or actively undergoing treatment for cancer.
12. Active seizure disorder or other significant neurological conditions other than migraine.
13. Myocardial infarction (MI), stroke, transient ischemic attack (TIA), unstable angina, or coronary artery bypass surgery or other revascularization procedure within 12 months prior to screening.
14. History or evidence of any other unstable or clinically significant medical condition that in the opinion of the sponsor-investigator/ Principal Investigator, would pose a risk to subject safety or interfere with the study evaluation, procedures or completion.
15. Evidence of drug or alcohol abuse or dependence within 12 months prior to screening, based on medical records or patient self-report.
16. Pregnant or breastfeeding, or expecting to conceive during the study, including through 16 weeks after the last dose of investigational product or placebo
17. Female subject of childbearing potential who is unwilling to use an acceptable method of effective contraception during treatment with investigational product or placebo through 16 weeks after the last dose of investigational product. Female subjects not of childbearing potential are defined as any female who is post-menopausal by history, defined as:
 - Age \geq 55 years with cessation of menses for 12 or more months, OR
 - Age $<$ 55 years but no spontaneous menses for at least 2 years, OR
 - Underwent bilateral oophorectomy, bilateral salpingectomy, or hysterectomy
18. Unlikely to be able to complete all protocol required study visits or procedures.
19. Currently receiving treatment in another investigational device or drug study.
- .

4.3 SCREEN FAILURES

Screening will occur at the baseline visit. Up to twenty screen failures are anticipated. The reason for screen failure will be documented.

Screen Failures are defined as:

- a) Patients who are not compliant with EMA or daily diary for more than 33% of triggered queries during the 30-day lead-in period.
- b) Patients who do not report at least 10 days of significant pain or pressure during the 30-day lead-in period.
- c) Patients needing prophylactic migraine medicine (meds listed under exclusion # 6) during the 30 day lead-in period.

4.4 STRATEGIES FOR RECRUITMENT AND RETENTION

Subjects will be recruited from Duke otolaryngologists and other clinicians who mainly treat sinus disease or facial pain. Clinic schedules will be pre-screened by the study coordinator several days in advance to ascertain potential subjects being seen for rhinosinusitis and/or facial pain. The study coordinator will alert providers of patients who appear potentially eligible based on pre-screening. If a patient is deemed eligible based on the exam and clinical findings, the study will be introduced by the provider when discussing treatment options for non-RS related facial pain. Referrals from outside clinics will also be taken and those patients will be assessed for eligibility. Recruitment brochures or flyers will be developed and posted in the waiting rooms of participating clinics and may be emailed to potential participants. Social media may be used to engage potential subjects outside of Duke. Once enrolled, subjects will be compensated \$100 for study visits 1 and 8, \$50 for visits 2-7, or \$500 for the entirety of the study.

5 STUDY INTERVENTION

5.1 STUDY INTERVENTION(S) ADMINISTRATION

5.1.1 STUDY INTERVENTION DESCRIPTION

Erenumab is a monoclonal antibody blocking the calcitonin gene-related peptide receptor. It is FDA-approved for the preventative treatment of migraine in adults. It is administered subcutaneously in the abdomen, thigh, or upper arm at a standard dose of 140 mg once a month.

5.1.2 DOSING AND ADMINISTRATION

Either erenumab 140 mg or placebo will be administered by a nurse in the Duke Otolaryngology clinic via subcutaneous injection in the abdomen, thigh, or upper arm. Study participants will receive monthly injections for six months. Prior to subcutaneous administration, study drug will sit at room temperature for at least 30 minutes protected from direct sunlight.

Currently, erenumab is not available in 140mg single dose syringes for this study. Subjects will receive either two 70mg erenumab injections for a total dose of 140mg of erenumab, or two injections of placebo.

5.2 PREPARATION/HANDLING/STORAGE/ACCOUNTABILITY

5.2.1 ACQUISITION AND ACCOUNTABILITY

Erenumab and matching placebo will be manufactured and supplied by Amgen, Inc. Study drug will be shipped directly from Amgen to the Duke Investigational Drug Service Pharmacy (IDS). Investigational product and placebo accountability including receipt, dispensation, and destruction will be recorded by IDS pharmacy using the electronic reporting system, Vestigo.

5.2.2 FORMULATION, APPEARANCE, PACKAGING, AND LABELING

Erenumab injection is a clear to opalescent, colorless to slightly yellow solution for subcutaneous administration. Erenumab for this study will be supplied as single dose pre-filled syringes containing 70 mg/mL solution. Placebo and active erenumab will be packaged in identical Type 1 glass syringes with attached stainless steel needle and labeled according to their contents. The unblinded IDS pharmacist or designee will dispense erenumab or matching placebo according to subject randomization schedule. Dispensed syringes will be indistinguishable in appearance and labeling to maintain the study blind.

5.2.3 PRODUCT STORAGE AND STABILITY

Erenumab for injection is stored at 2-8°C in the original carton to protect from light until time of use. If removed from the refrigerator, erenumab is stable for 7 days at room temperature 15-25°C. Erenumab syringes should not be frozen or shaken.

5.2.4 PREPARATION

Duke IDS pharmacist or designee will receive subject randomization number and match it to treatment assignment on unblinded randomization scheme. On day of dosing, IDS pharmacist will dispense assigned treatment (erenumab or placebo) with blinded labeling to study team for administration.

5.3 MEASURES TO MINIMIZE BIAS: RANDOMIZATION AND BLINDING

At the conclusion of the screening/lead-in period, eligible subjects will be randomly assigned to receive either erenumab 140 mg or placebo in a 1:1 allocation ratio based on a computer-generated randomization schedule supplied by the Duke IDS pharmacy. The subject, investigators, nurse, and study coordinator will be blinded.

5.4 STUDY INTERVENTION COMPLIANCE

Subjects will be administered the study drug or placebo each month in clinic by designated nurses. The nurse and study coordinator will monitor compliance at the time of medication administration. The study coordinator will review instructions on completing the daily log at each study visit. Reminder calls and/or messages via MyChart will be sent prior to each visit.

5.5 CONCOMITANT THERAPY

5.5.1 RESCUE MEDICINE

Rescue medicine for facial pain will be permitted. Recommendations by the principal investigator may consist of over-the-counter medications such as antihistamines, non-steroidal anti-inflammatory drugs, decongestants. Antibiotics and steroids may be indicated if clinical evidence for sinusitis exists. Patients will be referred to their primary care provider (PCP) for prescription medications including triptans, opiates, tramadol, acetaminophen-containing medications, butalbital. These medications are not commonly prescribed by otolaryngologists, and therefore, should be managed by the PCP. Subjects will be instructed to record rescue medicine intake in their EMA data log. The study coordinator or study team member will review all recorded rescue meds and query the patient regarding any rescue meds prescribed by another health care provider. The study coordinator or study team member will verify the rescue medications, by either review of the pill bottle or call to the PCP.

6 STUDY INTERVENTION DISCONTINUATION AND PARTICIPANT DISCONTINUATION/WITHDRAWAL

6.1 DISCONTINUATION OF STUDY INTERVENTION

Intervention will be discontinued in the event of a serious adverse reaction to the drug.

6.2 PARTICIPANT DISCONTINUATION/WITHDRAWAL FROM THE STUDY

Subjects will have the option of withdrawing from the study at any time for any reason. Reason and date for withdrawal, as well as any adverse events and concomitant medications since the last study visit will be documented.

The Principal Investigator may discontinue a subject from study treatment, or withdraw a patient from the study. Reasons for study treatment discontinuation or withdrawal may include but are not limited to the following:

- Adverse event or hypersensitivity reactions thought to be related to study drug (rash, angioedema, anaphylaxis, hypertensive crisis, persistently elevated blood pressure, constipation with serious complications).
- Patient voluntarily decides to withdraw.
- Patient non-compliance with the study protocol.
- Intercurrent disease, which in the opinion of the patient's treating physician, would affect the ability of the patient to continue on the clinical study.
- Patient lost to follow-up.

All subjects who received at least one dose of study drug or placebo will be requested to complete Visit 8, regardless of whether they completed the study, were withdrawn by the investigator or chose to withdrawal from the study.

Withdrawn and/or discontinued patients will be included in the data analysis by an intention to treat analysis.

6.3 LOST TO FOLLOW-UP

Subjects not appearing for their study visit will be contacted via telephone and, if necessary, by mail. A 10% dropout rate due to adverse events and loss of follow-up will be anticipated.

7 STUDY ASSESSMENTS AND PROCEDURES

7.1 EFFICACY ASSESSMENTS

Drug efficacy will be assessed through a smart-phone based app that queries daily symptoms and rescue medication use through EMA. Efficacy will also be assessed through disease-related questionnaires.

7.2 SAFETY AND OTHER ASSESSMENTS

Subjects will undergo history and physical exam at every visit to ensure drug safety. In addition, subjects will be asked specifically about the common adverse effects associated with erenumab, which include injection site reaction, constipation, and muscle spasm/cramps. Subjects will also be queried for hypersensitivity reactions and asked to monitor their blood pressure daily for 7 days after the first injection, weekly thereafter, and when symptomatic. The PI will assess the adverse events monthly or as needed for immediate intervention. A list of concomitant medications will also be recorded at each visit.

7.3 ADVERSE EVENTS AND SERIOUS ADVERSE EVENTS

7.3.1 DEFINITION OF ADVERSE EVENTS (AE)

An AE is any untoward medical occurrence in a clinical study subject. No causal relationship with the study drug or with the clinical study itself is implied. An AE can therefore be any unfavorable and unintended sign (including an abnormal finding), symptom, or disease temporally associated with the use of a medicinal (investigational) product, whether or not related to the medicinal (investigational) product. This includes any occurrence that is new in onset or aggravated in severity or frequency from the baseline condition, including abnormal results of diagnostic procedures and/or laboratory test abnormalities, which are considered AEs if they

- result in discontinuation from the study
- require treatment or any other therapeutic intervention
- require further diagnostic evaluation (excluding a repetition of the same procedure to confirm the abnormality)
- are associated with clinical signs or symptoms judged by the investigator to have a significant clinical impact

The investigator's clinical judgment is used to determine whether a subject is to be removed from treatment due to an adverse event. In the event a subject requests to withdraw from protocol-required therapies or the study due to an adverse event, refer to Section 6 for additional instructions on the procedures recommended for safe withdrawal from protocol-required therapies or the study.

7.3.2 DEFINITION OF SERIOUS ADVERSE EVENTS (SAE)

A Serious Adverse Event (SAE), as defined by the FDA, will be any adverse event that in the opinion of either the sponsor-investigator results in any of the following outcomes:

- 1) Death
- 2) Life-threatening adverse drug experience
- 3) Inpatient hospitalization or prolongation of existing hospitalization (for > 24 hours)
- 4) Persistent or significant incapacity or substantial disruption of the ability to conduct normal life functions
- 5) Congenital anomaly/birth defect

Of note, an Important Medical Event (IME) that may not result in death, be life threatening, or require hospitalization may be considered a serious adverse drug experience when, based upon medical judgment, it may jeopardize the patient or subject and may require medical or surgical intervention to prevent one of the outcomes listed in this definition

7.3.3 CLASSIFICATION OF AN ADVERSE EVENT

Unanticipated (Unexpected) Adverse Event:

An AE, the nature or severity of which is not consistent with the applicable product information (e.g., Investigator's Brochure) for an unapproved investigational product or package insert/summary of product characteristics for an approved product.

Adverse Event Associated With the Use of the Drug:

An AE is considered associated with the use of the drug if the attribution is possible, probable or definite.

7.3.3.1 SEVERITY OF EVENT

Assessment of Severity

The investigator will assess the intensity of the AE and rate the AE as mild, moderate, or severe using the Common Terminology Criteria for Adverse Events (CTCAE), Version 5, which can be accessed at: https://ctep.cancer.gov/protocolDevelopment/electronic_applications/docs/CTCAE_v5_Quick_Reference_5x7.pdf

The CTCAE classifies AEs as below:

- Grade 1 Mild; asymptomatic or mild symptoms; clinical or diagnostic observations only; intervention not indicated.
- Grade 2 Moderate; minimal, local or noninvasive intervention indicated; limiting age-appropriate instrumental ADL.

- Grade 3 Severe or medically significant but not immediately life-threatening; hospitalization or prolongation of hospitalization indicated; disabling; limiting self-care ADL.
- Grade 4 Life-threatening consequences; urgent intervention indicated.
- Grade 5 Death related to AE.

In addition, information pertaining to duration, treatment, and possibility of causality to study drug will be documented.

7.3.3.2 RELATIONSHIP TO STUDY INTERVENTION

The investigator's assessment of an AE's relationship to study drug will be part of the documentation process, but will not be a factor in determining what is or is not reported in the study. If there is any doubt as to whether a clinical observation is an AE, the event should be reported.

The investigator will assess the relationship or association of the study drug in causing or contributing to the AE, which will be characterized using the following classification and criteria:

Definite: Adverse events that, after careful medical evaluation, are considered definitely related to the study drug, and other conditions (concurrent illness, progression/expression of disease state, or concurrent medication reaction) do not appear to explain the event.

Probable: Adverse events that, after careful medical evaluation, are considered with a high degree of certainty to be related to the study drug. The following characteristics will apply:

- A reasonable temporal relationship exists between the event and exposure to the study drug, and
- The event is a known reaction to the study drug that cannot be explained by an alternative cause commonly occurring in the population/individual, or
- The event is not a known reaction to the study drug but cannot be reasonably explained by an alternative cause.

Possible: Adverse events that, after careful medical evaluation, do not meet the criteria for a definite or probable relationship to the study drug, but for which a connection cannot be ruled out with certainty. The following characteristics will apply:

- The event occurs after exposure to the study drug, and
- There is a reasonable temporal relationship to the application, but the event is not a known reaction to the study drug and could be explained by a commonly occurring alternative cause, or
- In the absence of a reasonable temporal relationship, the event cannot be explained by an alternative cause.

Unlikely: Adverse events that, after careful medical evaluation, do not meet the criteria for a possible, probable or definite relationship to the study drug and for which a connection is unlikely. The following characteristics will apply:

- The event does not follow a reasonable temporal sequence from administration of the study drug, or
- The event may have been produced by environmental factors, and
- There is no apparent pattern of response to the study drug.

Not related: Adverse events in this category will have either of the following characteristics:

- The event occurs before exposure to the study drug, or
- The event does not have a reasonable temporal relationship to study drug administration and can be explained by a commonly occurring alternative cause.

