Development of hypertension and worsening of pre-existing hypertension have been reported following the use of Aimovig® in the postmarketing setting. Many of the patients had pre-existing hypertension or risk factors for hypertension. There were cases requiring pharmacological treatment and, in some cases, hospitalization. Hypertension may occur at any time during treatment but was most frequently reported within seven days of dose administration. In the majority of the cases, the onset or worsening of hypertension was reported after the first dose. Aimovig® was discontinued in many of the reported cases.

We will monitor patients treated with Aimovig® for new-onset hypertension, or worsening of pre-existing hypertension, and consider whether discontinuation of Aimovig® is warranted if evaluation fails to establish an alternative etiology.

The pre-filled syringe may cause pain or discomfort in addition to bleeding, bruising, redness, warmth, itching, swelling, infection, or firmness of the skin near the injection site. Additionally, the pre-filled syringe contains a dry natural rubber that is derived from latex, which may cause an allergic reaction. Subjects who have a known allergy to latex will be excluded.

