9.1.2 DISCONTINUATION AND STUDY STOPPING RULES

Subjects will be given the opportunity to withdraw from the study at any time. Every effort will be made to obtain follow-up information. Subjects who discontinue prematurely will be asked to return for a final follow-up visit either in person or by phone.

In the event of serious adverse events felt to be possibly related to erenumab and occurring in more than 3 study patients, the study will stop enrollment and the FDA will be notified for review and feedback. A single patient death possibly related to erenumab will also stop the study.

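### The causality scale gives no counted category to a known, well-timed erenumab reaction that also has a common alternative cause, so such serious events could be left out of the possibly-related stopping count

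*Combined protocol and SAP*

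**What the plan says.** Section 7.3.3.2 sets five levels of relationship and, for all but Definite, lists characteristics that are to hold.

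- **Definite:** other conditions "do not appear to explain the event".
- **Probable:** reasonable timing, plus one of two limbs. The limb for known reactions reads: "The event is a known reaction to the study drug that cannot be explained by an alternative cause commonly occurring in the population/individual". Its counterpart takes reactions not previously known, again only where no other cause reasonably accounts for them.
- **Possible:** onset after exposure, plus one of two limbs. In the first, timing is reasonable, "but the event is not a known reaction to the study drug and could be explained by a commonly occurring alternative cause". In the second, timing is not reasonable and no alternative cause accounts for the event. A lead-in describes the level more generally, as events short of Definite or Probable for which a link to the drug cannot be excluded for certain.
- **Unlikely:** no reasonable time sequence, or possible environmental causes, joined to the absence of any pattern of response to the drug.
- **Not related:** onset before exposure, or "The event does not have a reasonable temporal relationship to study drug administration and can be explained by a commonly occurring alternative cause".

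Section 7.3.3 (Classification of an Adverse Event) then draws the line: "An AE is considered associated with the use of the drug if the attribution is possible, probable or definite". Section 9.1.2 stops enrollment and notifies the FDA in the event of "serious adverse events felt to be possibly related to erenumab and occurring in more than 3 study patients". It also stops the study for one death possibly related to erenumab.

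**The concern.** On a causality scale, the fact that an event is already known to follow the drug should raise its attribution or leave it unchanged. Here the first limb of Possible does the reverse: with the same timing and the same alternative cause, an unknown reaction is Possible and a known one is not.

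The affected events are of a kind the protocol itself names. Section 2.3.1 describes post-marketing hypertension, most often within seven days of a dose and sometimes leading to hospitalization, and says: "Many of the patients had pre-existing hypertension or risk factors for hypertension". It also describes constipation with serious complications, at higher risk in people taking medicines that slow the gut, and 5.5.1 lists opiates among possible rescue medicines. Section 4.2 excludes uncontrolled or unstable blood pressure, but 3.2.2 provides for participants whose baseline pressure is abnormal.

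At stake is the count in 9.1.2, the only numerical aggregate safety trigger in the documents, together with the single-death trigger beside it.

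**Working it through.** The documents state no operating characteristic for the stopping rule, so there is no figure to reproduce. The check is one of logic, followed by an illustration.

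**Step 1: code the criteria.** For an event after exposure, let K = known reaction, T = reasonable timing, A = common alternative cause. From the bullets in 7.3.3.2:

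- Definite: requires not A
- Probable: T and not A, whether or not K
- Possible: (T and not K and A) or (not T and not A)
- Not related: not T and A
- Unlikely: not T, or (environmental factors and no response pattern)

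**Step 2: run all 2 × 2 × 2 = 8 combinations.**

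| K | T | A | Category met | Counted as drug-associated? |
|---|---|---|---|---|
| yes | yes | no | Definite or Probable | yes |
| no | yes | no | Definite or Probable | yes |
| no | yes | yes | Possible | yes |
| **yes** | **yes** | **yes** | **none, unless the environmental and no-pattern conditions make it Unlikely** | **no** |
| yes | no | no | Possible (Unlikely also arguable) | yes, if Possible |
| no | no | no | Possible (Unlikely also arguable) | yes, if Possible |
| yes | no | yes | Not related or Unlikely | no |
| no | no | yes | Not related or Unlikely | no |

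The conditional route to Unlikely is open in the other well-timed rows too, but those rows also have a counted category.

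**Step 3: vary the reading.** The and/or bullets can be grouped differently: the no-pattern condition can govern all of Unlikely, and the second limb of Probable can stand without the timing condition. Under that grouping, Unlikely becomes conditional in every row and the no/no/no row can also be Probable. The yes/yes/yes row does not change.

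**Step 4: test the repair.** If the first limb of Possible becomes (T and A), whatever K is, the yes/yes/yes row moves to Possible. The other seven rows keep their categories.

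**Step 5: what lost events could do to the count.** More than 3 patients means 4 or more. If exactly four patients qualify, one uncounted event keeps the rule from firing. For the death trigger, a single attribution decides.

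As an illustration only, let N patients each have probability p of a qualifying SAE, with a fraction m of these uncounted. Then P(rule fires) = P(X ≥ 4), where X is binomial with parameters N and p(1 − m). Section 3.1 randomizes 66 patients 1:1, so N = 33 on erenumab. The values of p and m are assumptions; neither is in the documents.

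| p | m = 0 | m = 0.25 | m = 0.5 |
|---|---|---|---|
| 0.05 | 0.081 | 0.034 | 0.009 |
| 0.10 | 0.423 | 0.233 | 0.081 |
| 0.20 | 0.919 | 0.750 | 0.423 |

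Attribution is made blind (7.3.4), so events in both arms may be rated. With N = 66 and p = 0.05 the figures are 0.421, 0.235 and 0.083.

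**The case against.** The strongest reply is that the lead-in to Possible fits this case: the event falls short of Probable, and a link to the drug cannot be excluded. An investigator who relies on it would count the event. That stands as a reason the loss is not certain. It does not remove the defect, because the text goes on to say that the listed characteristics apply, and they leave the event out. Two raters could follow the same page and disagree.

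Second, 9.1.2 speaks of what is felt to be possibly related and does not cite the scale. That is correct. The link is an inference from the shared term and from the dividing line in 7.3.3.

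Third, a risk factor is not the same as an alternative cause. Section 2.3.1 lists worsening of pre-existing hypertension as itself a reported reaction, and says gut-slowing medicines may raise the chance of constipation, not that they explain it in place of erenumab. A predisposed patient's event may still be Probable. A reader might infer that the gap captures the typical hypertension or constipation case; the documents do not support that. Section 4.2 also excludes uncontrolled blood pressure and several antihypertensive drugs during the lead-in.

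Fourth, a reader might infer that FDA expedited reporting is compromised. The test in 7.3.5 requires the event to be unexpected as well as possibly related, and a known reaction is generally expected. At most this matters where severity goes beyond the product information.

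Fifth, frequency may be low. The 3% constipation rate in 2.3.1 gives 33 × 0.03 = 0.99, about one case of any severity on erenumab. No rate of serious events is given, and one row in eight is a count of logical cases, not a frequency.

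**Conclusion.** The point holds as a defect in a written rule. A known, well-timed reaction with a common alternative cause meets no criterion for Definite, Probable, Possible or Not related, and being a known reaction lowers its attribution. This result does not depend on how the and/or bullets are grouped.

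The consequence is a possibility: some serious known reactions could be left out of the drug-associated class and, if 9.1.2 is applied through the scale, out of the stopping count and the death trigger. How often is unknown, since the probabilities shown rest on assumed rates.

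A reader might also infer that such events would be rated Not related; reasonable timing rules that out. Nor does the gap hide events or leave individuals unprotected. Section 7.3.3.2 says attribution does not decide what is reported, 7.3.4 records every AE, 7.3.5 sends SAEs to the manufacturer and the IRB regardless of cause, and the blood-pressure removal provisions in 3.2.2 involve no attribution step. What can be lost is the count, not the data.

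**What to change.** 1. In 7.3.3.2, reword the reasonable-timing limb of Possible so that it covers an event that a commonly occurring alternative cause could explain, whether or not it is a known reaction to the study drug. Leave the other categories as they are.
2. In 9.1.2, state that possibly related means an attribution of possible, probable or definite under 7.3.3.2, for both the patient count and the death trigger. The first change alone would leave the stopping rule unconnected to the scale.
3. If events have already been classified, re-check, still blinded, those that are known reactions with reasonable timing.

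The cost is a short protocol amendment and somewhat more AEs labelled possibly related. The threshold of more than 3 patients is untouched.
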